4.3. Criteria for Temporarily Delaying Vaccine Administration

The following conditions are temporary or self-limiting and a subject may be vaccinated once the condition(s) has/have resolved and no other exclusion criteria are met:

1. Current febrile illness (oral temperature of $\geq 38.0^{\circ}\text{C}$ [100.4°F]) or other acute illness within 48 hours prior to investigational product administration.
2. Subject has received seasonal or pandemic influenza vaccine within the previous 14 days or any other nonstudy vaccine within the previous 28 days before investigational product administration.
3. If systemic corticosteroids have been administered short term (≤ 7 days) for treatment of an acute illness, investigational product administration should be delayed until systemic corticosteroid use has been discontinued for at least 28 days. Inhaled, intra-articular/intrabursal, or topical corticosteroids are permitted.

If a subject meets any delay criteria for vaccination, all study procedures, including blood sample collection relating to that visit, should be delayed until the day of vaccination.

4.4. Lifestyle Requirements

4.4.1. Contraception

All fertile male subjects who are, in the opinion of the investigator, sexually active and at risk for pregnancy with their partner(s) must agree to use a highly effective method of contraception consistently and correctly for the duration of the vaccination period and for at least 28 days after the last dose of investigational product. The investigator or his or her designee, in consultation with the subject, will confirm that the subject has selected an appropriate method of contraception for the individual subject and his partner from the permitted list of contraception methods (see below) and will confirm that the subject has been instructed in its consistent and correct use. At time points indicated in the [schedule of activities](#), the investigator or designee will inform the subject of the need to use highly effective contraception consistently and correctly and document the conversation and the subject's affirmation in the subject's chart (subjects need to affirm their consistent and correct use of at least 1 of the selected methods of contraception). In addition, the investigator or designee will instruct the subject to call immediately if the selected contraception method is discontinued or if pregnancy is known or suspected in the partner.

Highly effective methods of contraception are those that, alone or in combination, result in a failure rate of less than 1% per year when used consistently and correctly (ie, perfect use) and include the following:

1. Established use of hormonal methods of contraception associated with inhibition of ovulation (eg, oral, inserted, injected, implanted, transdermal), provided the male subject's female partner plans to remain on the same treatment throughout the entire study and has been using that hormonal contraceptive for an adequate period of time to ensure effectiveness.
2. Correctly placed copper-containing intrauterine device (IUD).
3. Male condom or female condom used WITH a separate spermicide product (ie, foam, gel, film, cream, or suppository). For countries where spermicide is not available or condom plus spermicide is not accepted as highly effective contraception, this option is not appropriate.
4. Male sterilization with absence of sperm in the postvasectomy ejaculate.
5. Bilateral tubal ligation/bilateral salpingectomy or bilateral tubal occlusive procedure (provided that occlusion has been confirmed in accordance with the device's label).
6. Female partner who meets the criteria for nonchildbearing potential, as described below:
 - Have undergone a documented hysterectomy and/or bilateral oophorectomy;
 - Have medically confirmed ovarian failure; or

- Achieved postmenopausal status, defined as follows: cessation of regular menses for at least 12 consecutive months with no alternative pathological or physiological cause.

NOTE: Sexual abstinence, defined as completely and persistently refraining from all heterosexual intercourse (including during the entire period of risk associated with the study treatments) may obviate the need for contraception ONLY if this is the preferred and usual lifestyle of the subject.

4.5. Sponsor's Qualified Medical Personnel

The contact information for the sponsor's appropriately qualified medical personnel for the study is documented in the study contact list located in the study reference manual (SRM).

To facilitate access to appropriately qualified medical personnel on study-related medical questions or problems, subjects are provided with a contact card. The contact card contains, at a minimum, protocol and investigational product identifiers, subject study numbers, contact information for the investigator site, and contact details for a contact center in the event that the investigator site staff cannot be reached to provide advice on a medical question or problem originating from another healthcare professional not involved in the subject's participation in the study. The contact number can also be used by investigator staff if they are seeking advice on medical questions or problems; however, it should be used only in the event that the established communication pathways between the investigator site and the study team are not available. It is therefore intended to augment, but not replace, the established communication pathways between the investigator site and the study team for advice on medical questions or problems that may arise during the study. The contact number is not intended for use by the subject directly, and if a subject calls that number, he or she will be directed back to the investigator site.

5. INVESTIGATIONAL PRODUCTS

For the purposes of this study, and per International Council for Harmonisation (ICH) guidelines, investigational product is defined as a pharmaceutical form of an active ingredient or placebo being tested or used as a reference/comparator in a clinical trial, including a product with a marketing authorization when used or assembled (formulated or packaged) in a way different from the approved form, or when used for an unapproved indication, or when used to gain further information about an approved use (ICH E6 1.33).

For this study, the investigational products are *C difficile* vaccine and placebo (saline). Since the appearance of these investigational products is not identical, the study is observer-blinded. The 3 lots of *C difficile* vaccine will appear identical and all site personnel will be blinded to lot allocation.

5.1. Allocation to Investigational Product

Allocation of subjects to vaccine groups will proceed through the use of an interactive response technology (IRT) system (interactive Web-based response [IWR]) in a randomization ratio of 1:1:1:1 to each of the lots and control group. Study personnel (either

blinded or unblinded) will be required to enter or select information including but not limited to the user's identification (ID) and password, the protocol number, and the subject number. They will then be provided with a randomization number, vaccine assignment, and dispensable unit (DU) or container number. The IRT system will provide a confirmation report containing the subject number, randomization number, and DU or container number assigned. The confirmation report must be retained by the unblinded dispenser in the unblinded site files.

The study-specific IRT reference manual will provide the contact information and further details on the use of the IRT system.

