5.2. Blinding of Site Personnel

In this observer-blinded study, the study staff dispensing and administering the vaccine will be unblinded, but all other site study personnel, including the principal investigator and the subject, will be blinded.

The principal investigator will assign the responsibility of the unblinded dispensers/administrators to persons who will not participate in the evaluation of any study subject. To ensure adequate coverage, at least 2 unblinded dispensers/administrators will be assigned per site. Members of the study site staff or clinic pharmacy should fulfill these roles. Contact between the unblinded dispensers and study subjects should be kept to a minimum. The investigator, study coordinator, and any site staff other than the unblinded dispensers/administrators must not be allowed to know the investigational product assigned to any study subject and must not be allowed to see the investigational product container contents.

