5.4. Breaking the Blind

The study will be subject and investigator blinded.

At the initiation of the study, the investigator site will be instructed on the method for breaking the blind. The method will be an electronic process. Blinding codes should be broken only in exceptional circumstances when knowledge of the actual vaccine assignment is absolutely essential for further management of the subject. Investigators are encouraged to discuss with a member of the study team if they believe that unblinding is necessary. When the blinding code is broken, the reason must be fully documented and entered on the case report form (CRF).

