6. STUDY PROCEDURES

6.1. Study Period

6.1.1. Visit 1: Month 0 – Vaccination 1 (Day 1)

It is anticipated that the procedures below will be conducted in a stepwise manner; ensure that procedures listed prior to administration of the vaccine are conducted prior to vaccination.

- Obtain written informed consent prior to performing any protocol-required procedures.
- Record the subject's demography (including date of birth, sex, race, and ethnicity). The date of birth will be collected to critically evaluate the immune response and safety profile by age.
- Conduct a clinical assessment, including review of medical history, to verify that all inclusion criteria, none of the exclusion criteria, and none of the temporary delay criteria are met ([Section 4](#)). Record medical history of significance, including the presence of chronic medical conditions. If the clinical assessment indicates that a physical

examination is necessary to comprehensively evaluate the subject, perform a physical examination and record the findings.

- Record nonstudy vaccines as described in [Section 5.9.1](#).
- Measure and record the subject's weight and height.
- Measure and record the subject's oral temperature.
- Discuss contraceptive use.
- Ensure that all inclusion criteria, none of the exclusion criteria, and none of the temporary delay criteria are met ([Section 4](#)).
- An appropriate site staff member (may be blinded or unblinded) will use the IRT system to obtain the subject's randomization number and investigational product blinded carton number.
- Collect a blood sample of approximately 20 mL for immunogenicity testing ([Section 7.2](#)).
- Unblinded site staff will prepare and administer investigational product. Investigational product will be administered by intramuscular injection into the upper deltoid muscle, preferably of the nondominant arm. The time of vaccination will be recorded. Refer to the IP manual under separate cover for further instruction on this process.
- The unblinded vaccine dispenser/administrator updates the investigational product accountability records.
- Blinded study staff will observe the subject for at least 30 minutes after investigational product administration for any acute reactions. Any AEs noted during the observation period should be recorded in the CRF.
- Record and report AEs and serious adverse events (SAEs) (relative to the time of vaccination) as described in [Section 8](#) and the [schedule of activities](#).

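### Does Protocol 5.1 let blinded site staff see the vaccine assignment in the IRT system?

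*Protocol*

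**What the plan says.** Protocol 5.1 describes allocation through the IRT system. The users are study personnel who may be blinded or unblinded, and after they enter their details, "They will then be provided with a randomization number, vaccine assignment, and dispensable unit (DU) or container number". The same paragraph then describes the document that the system issues: "The IRT system will provide a confirmation report containing the subject number, randomization number, and DU or container number assigned". That report is kept by the unblinded dispenser in the unblinded site files.

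Protocol 5.2 sets the blinding rule. The investigator, the coordinator and all other site staff except the unblinded dispensers and administrators "must not be allowed to know the investigational product assigned to any study subject". The dispensing role goes "to persons who will not participate in the evaluation of any study subject". The opening of Protocol 5 adds that "all site personnel will be blinded to lot allocation". Under Protocol 5.4 the blind may be broken "only in exceptional circumstances when knowledge of the actual vaccine assignment is absolutely essential".

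Protocol 6.1.1 gives the working instruction for Visit 1: a staff member, blinded or not, uses the IRT to obtain the subject's "randomization number and investigational product blinded carton number". Sections 6.1.2 and 6.1.4 say the same for Visits 2 and 4, with the carton number alone. Sections 5.6.1.1 and 5.6.1.2 state that vaccine and placebo are both supplied in sealed, blinded cartons.

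**The concern.** The two sections cannot both be followed to the letter when the IRT user is blinded. Section 5.1 hands that person the *vaccine assignment*, and section 5.2 says that person may not know it. The phrase is hard to read as another name for the carton code, because the sentence lists the container number as a separate item. If the assignment named the lot, even the unblinded dispensers would learn something that Protocol 5 withholds from all site personnel.

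The stakes would lie in the safety data. Vaccine and saline do not look alike, so the observer blind depends on procedure. Staff who evaluate subjects are blinded by design, and blinded staff carry out the observation after each injection. A person who knew the allocation could elicit or record adverse events differently (Protocol 8.1.2) or judge causality differently (Protocol 8.1.5). Adverse event counts feed the incidence summaries and the Tier 1 and Tier 2 comparisons of pooled lots with placebo in SAP 3.5.1. Causality feeds the summary of related events.

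**Working it through.** No arithmetic bears on this point, so the check is to set the texts side by side.

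**What the IRT returns**

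| Place | Event described | Assignment listed? |
|---|---|---|
| Protocol 5.1, output to the user | Randomization | Yes |
| Protocol 5.1, confirmation report | Randomization | No |
| Protocol 6.1.1, Visit 1 | Randomization | No |
| Protocol 6.1.2, Visit 2 | Later dispensing | No |
| Protocol 6.1.4, Visit 4 | Later dispensing | No |

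The last two rows carry less weight. Randomization happens once, at Visit 1, so those visits would not be expected to repeat its output; they omit the randomization number as well. The fair comparison is the first three rows, where 1 of 3 lists the assignment. Adding the later visits gives 1 of 5. Either count shows which sentence is the outlier; neither measures an effect.

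**Which text governs conduct.** Section 5.2 is a direct prohibition. Sections 6.1.1, 6.1.2 and 6.1.4 are the instructions that staff carry out, and each expressly allows a blinded user while naming only blinded identifiers. Sealed, blinded cartons for both products make sense only if the carton number does not reveal the contents. All of these agree with one another, and only two words in section 5.1 do not.

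**Whether the other suggested conflicts add anything.** Section 5.4 speaks of the *actual* assignment. That adjective leaves room for a coded assignment in the IRT that differs from the identity revealed by code-breaking, and the documents do not define either term. The conflict with lot blinding arises only if the displayed item names a lot, which section 5.1 does not say.

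**What must happen for harm.** Three things must all be true:

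1. The IRT displays the product identity.
2. It does so to a blinded user.
3. That user then elicits adverse events or judges causality.

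The documents establish none of the three. Section 6.1.1 asks only for an appropriate staff member and does not make the IRT user the evaluator.

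**What is out of reach in any case.** Laboratory staff who run the serology assays stay blinded (Protocol 5.3), so the primary immunogenicity endpoint is largely protected. Local reactions and systemic events are recorded by subjects in the e-diary (Protocol 7.1.1), which largely protects them from observer knowledge. The 263 evaluable subjects per lot, the (0.5, 2) interval and the 95% confidence level do not depend on the sentence.

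**The case for a change.** The best case for a correction is that section 5.1 is the dedicated allocation section and leaves the remaining detail to an IRT reference manual that is not among the documents. The reader therefore cannot confirm that the system departs from the words of section 5.1. Showing that one sentence is the odd one out does not make the texts consistent, and deleting two words costs little. There is also an oddity: the confirmation report, which lists no assignment, is reserved for the unblinded files, while the more sensitive item is said to go to any user.

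Part of this stands. The literal mismatch between sections 5.1 and 5.2 is certain, and the actual screen output cannot be verified from the protocol and SAP. The step from there to a needed change does not follow. The prohibition in section 5.2 already binds the IRT configuration, whatever section 5.1 lists, and the visit instructions already tell staff what to obtain. Editing section 5.1 would alter nothing that a compliant site does. Holding the report in unblinded files is a precaution that points towards protecting the blind. The edit would also be a protocol amendment needing ethics approval under Protocol 12.1. SAP Table 1 already reacts to data that turned out not to be available, which suggests that conduct was well advanced by SAP Version 3; if so, rewording would reach few subjects or none.

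**Conclusion.** This is a clerical slip in one sentence of Protocol 5.1. The contradiction with section 5.2 exists on a literal reading, but the rest of the protocol settles how the IRT is to be used, and it does so in favour of the blind. No unblinding is shown. The size of any bias cannot be computed from the documents, and the path to one is hypothetical and confined to investigator-recorded adverse events and causality. The lot-consistency conclusion is untouched.

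The conclusion rests on one assumption: that the IRT was configured to match section 5.2 and the visit procedures. Confirming role permissions against the blinding rule is ordinary system set-up and can be done without altering the plan. If that check showed the assignment on a blinded user's screen, the fault would be a breach of section 5.2 in the system configuration and would need handling as such. On the documents as they stand, no change to the design, the analysis or the interpretation follows.

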5.2. Blinding of Site Personnel

In this observer-blinded study, the study staff dispensing and administering the vaccine will be unblinded, but all other site study personnel, including the principal investigator and the subject, will be blinded.

The principal investigator will assign the responsibility of the unblinded dispensers/administrators to persons who will not participate in the evaluation of any study subject. To ensure adequate coverage, at least 2 unblinded dispensers/administrators will be assigned per site. Members of the study site staff or clinic pharmacy should fulfill these roles. Contact between the unblinded dispensers and study subjects should be kept to a minimum. The investigator, study coordinator, and any site staff other than the unblinded dispensers/administrators must not be allowed to know the investigational product assigned to any study subject and must not be allowed to see the investigational product container contents.

5.3. Blinding of the Sponsor

Those study team members who are involved in ensuring that protocol requirements for investigational product handling, allocation, and administration are fulfilled at the site (eg, the unblinded Pfizer clinician [separate from the study team], clinical research associates [CRAs]) will be unblinded for the duration of the study. All other study team members and all laboratory personnel performing the serology assays will remain blinded to vaccine assigned/received throughout the study.

5.4. Breaking the Blind

The study will be subject and investigator blinded.

At the initiation of the study, the investigator site will be instructed on the method for breaking the blind. The method will be an electronic process. Blinding codes should be broken only in exceptional circumstances when knowledge of the actual vaccine assignment is absolutely essential for further management of the subject. Investigators are encouraged to discuss with a member of the study team if they believe that unblinding is necessary. When the blinding code is broken, the reason must be fully documented and entered on the case report form (CRF).

5.5. Subject Compliance

All doses of investigational product will be administered by the appropriately designated unblinded study staff at the investigator site.

5.6. Vaccine Supplies

5.6.1. Formulation and Packaging

5.6.1.1. *Clostridium difficile* Vaccine

The investigational *C difficile* vaccine is toxoid based. *C difficile* toxin A and toxin B are inactivated by a combination of genetic mutations and chemical treatments. The vaccine is provided as a sterile lyophilized powder in a dosage strength of 200 µg/dose (total for toxoids A and B). The vaccine will be reconstituted with ALOH diluent immediately before use as instructed in the investigational product (IP) manual. The ALOH diluent is supplied as a 1-mg aluminum/mL (as ALOH) liquid suspension.

Blinded, sealed cartons will contain 1 single-use vial of *C difficile* vaccine lyophilized powder for reconstitution and 1 single-dose syringe of ALOH diluent. The total volume of resuspended vaccine to be injected is 0.5 mL per dose.

The investigational products will be provided by the sponsor to each study site. Investigational product and diluent will be packed and labeled by Pfizer or its designee as investigational product in accordance with current guidelines and applicable local and legal regulatory requirements. For detailed information on the antigenic components of the investigational product, please refer to the IB.

5.6.1.2. Placebo

The placebo will consist of a sterile normal saline solution for injection (0.9% sodium chloride injection, in a 0.5-mL dose) and will be provided by the sponsor to each study site. The placebo will be packaged within cartons labeled by Pfizer or its designee in accordance with current guidelines and applicable local and legal regulatory requirements. Blinded, sealed cartons will contain 1 single-dose syringe of placebo. Refer to the IP manual for details regarding the preparation and dispensing of placebo.

5.6.2. Preparation and Dispensing

Refer to the IP manual for instructions on how to prepare the investigational product for administration. Investigational product should be prepared and dispensed by an appropriately qualified and experienced **unblinded** member of the study staff.

5.6.3. Administration

All injections will be administered in the upper deltoid muscle, preferably of the nondominant arm, by the **unblinded** administrator. The size of the needle used for administration will be based on the subject's weight at the time of enrollment. Refer to the IP manual for additional information.

Subjects will receive 1 dose of *C difficile* vaccine/placebo at Visits 1 (Month 0), 2 (Month 1), and 4 (Month 6).

Standard vaccination practices must be observed and vaccine must not be injected into blood vessels. Appropriate medication and other supportive measures for management of an acute hypersensitivity reaction should be available in accordance with local guidelines for standard immunization practices.

Administration of investigational products should be performed by an appropriately qualified, Good Clinical Practice (GCP)-trained, and vaccine-experienced member of the study staff (eg, physician, nurse, physician's assistant, nurse practitioner, pharmacist, or medical assistant) as allowed by local, state, and institutional guidance.

Investigational product administration details will be recorded on the CRF.

